16.3 Appendix 3: Pharmacokinetic sampling

Table 16-5 PK Sampling scheme

| Time (post first dose)* | 1 h | 2 h | 62 h | 66 h | 68 h | 84 h | 168 h |
|-------------------------|-----|-----|------|------|------|------|-------|
| Sample number | 101 | 102 | 103 | 104 | 105 | 106 | 107 |
| Scheme n°1 | X | X | X | X | | | X |
| Scheme n°2 | X | X | | | X | X | X |

*Dosing times are 0, 8, 24, 36, 48 and 60 h

Perform the PK blood collection as outlined in the assessment schedule assigned to the patient (Table 16-4).

Methodology for whole blood sampling:

Blood samples will be taken by either direct venipuncture or an indwelling cannula inserted in a forearm vein.

Handling of blood samples for plasma collection:

Artemether is rapidly degraded in whole blood and by products of haemolysis in plasma. It is essential that the samples are handled as follows:

- Collect 500 µL blood in K2EDTA.
- Immediately after each tube is drawn (within 5 minutes after collection), the sample should be inverted gently several times to ensure mixing and centrifuged at 4°C at 4000 rpm (2200 g) for 10min.
- Remove plasma (about 200 µL should be obtained) quickly and transfer into polypropylene, screw cap tubes (NUNC barcoded 1D plus 2D tubes from ThermoFischer).
- Freeze aliquots immediately at $\leq -70^{\circ}\text{C}$ until analysis. No interim freezing at lower temperature should be done. If necessary, storage on dry ice for no more than one hour is acceptable.

The actual sample collection date and time will be entered on the PK blood collection page of the (e)CRF. Sampling problems will be commented on in the (e)CRFs.

16.4 Appendix 4: Signs and symptoms indicative of severe *P. falciparum* malaria (WHO 2015)

In a patient with *P. falciparum* asexual parasitaemia and no other obvious cause of symptoms, the presence of one or more of the following clinical or laboratory features classifies the patient as suffering from severe malaria. These severe manifestations can occur singly or, more commonly, in combination in the same patient. The full clinical picture should be considered rather than just one isolated parameter.

Clinical Features:

- Impaired consciousness A Glasgow coma score < 11 in adults or a Blantyre coma score < 3 in children.

- Prostration, i.e. generalized weakness so that the patient is unable walk or sit up without assistance.
- Multiple convulsions – more than two episodes in 24 h
- Deep breathing, respiratory distress (acidotic breathing)
- Shock: compensated shock is defined as capillary refill \geq 3s or temperature gradient on leg (mid to proximal limb), but no hypotension. Decompensated shock is defined as systolic blood pressure $<$ 70 mm Hg in children or $<$ 80 mm Hg in adults, with evidence of impaired perfusion (cool peripheries or prolonged capillary refill).
- Clinical jaundice plus evidence of other vital organ dysfunction: plasma or serum bilirubin $>$ 50 μ mol/L (3 mg/dL) with a parasite count $>$ 100 000/ μ L.
- Abnormal spontaneous bleeding: including recurrent or prolonged bleeding from the nose, gums or venepuncture sites; haematemesis or melaena.
- Pulmonary oedema: radiologically confirmed or oxygen saturation $<$ 92% on room air with a respiratory rate $>$ 30/min, often with chest indrawing and crepitations on auscultation.

Laboratory findings

- Hypoglycemia (blood or plasma glucose $<$ 2.2 mmol/L or $<$ 40 mg/dL)
- Severe malaria anaemia: haemoglobin concentration \leq 5g/dL or a haematocrit of \leq 15% in children $<$ 12 years of age ($<$ 7g/dL and $<$ 20%, respectively, in adults) with a parasite count $>$ 10 000/ μ L.
- Acidosis: a base deficit of $>$ 8 mEq/L or, if not available, a plasma bicarbonate level of $<$ 15 mmol/L or venous plasma lactate \geq 5 mmol/L.
- Hyperparasitaemia: P.Falciparum parasitaemia $>$ 10%
- Renal impairment: plasma or serum creatinine $>$ 265 μ mol/L (3 mg/dL) or blood urea $>$ 20 mmol/L.

16.5 Appendix 5: IMCI guidelines

Infants aged >2 months– check for danger signs

1. Not able to drink or breast feed
 - Too weak to drink and is not able to suck or swallow when offered a drink or breast-fed
 - If not sure ask mother to offer child a drink of clean water or breast milk
 - A child may have difficulty sucking when his nose is blocked. If the nose is blocked, clean
2. Vomiting everything
 - A child is not able to hold anything down at all
 - If in doubt offer the child water
3. Convulsions (during this illness)
 - Arms and legs stiffen because muscles are contracting
 - The child may lose consciousness or not be able to respond to spoken directions or handling, even if eyes are open

- “Fits” or “spasms” or “jerky movements”

Note: shiver is not a convulsion. There is no loss of consciousness.

4. Abnormally sleepy or difficult to awaken

- Drowsy and does not show interest in what is happening around him
- Stare blankly and appear not to notice what is going on around him
- Does not respond when touched, shaken or spoken to

Note: If the child is asleep and has cough or difficult breathing, count the number of breaths before you try to wake the child.

Infants aged 0- 2 months- check for signs of bacterial infection (except for fever: 37.5°C* or above)

Possible serious bacterial infection

- Convulsions
- Fast breathing (60 breaths per minute or more)
- Severe chest indrawing
- Nasal flaring
- Grunting
- Bulging fontanelle
- Pus draining from ear
- Umbilical redness extending to the skin
- Low body temperature (less than 35.5 °C* or feels cold)
- Many or severe skin pustules
- Lethargic or unconscious
- Less than normal movement

*These thresholds are based on axillary temperature. The thresholds for rectal temperature readings are approximately 0.5 °C higher

Possible local bacterial infection

- Red umbilicus
- Draining pus
- Skin pustules

The purpose of this Statistical Analysis Plan (SAP) is to describe the implementation of the statistical analysis which is planned in the protocol. This study is composed of two cohorts, Cohort 1 consisting of infants aged more than 28 days (<5kg) and Cohort 2 consisting of neonates aged 28 days or less (<5kg). After the core period of each Cohort an interim assessment will be performed by Novartis and results presented to an independent Data Monitoring Committee (DMC). Potential outputs for the DMC will be included in the CSR TFL shell document. No separate SAP or TFL shell document will be prepared for the interim assessments. This SAP will be used as a basis for the clinical study report, which will be prepared after the final database lock (DBL).

1.1 Study design

This is a multicenter, open-label, single-arm, adaptive design with dose adaptation (de-escalation or escalation) study in infants and neonates <5 kg body weight with *P. falciparum* malaria.

A total of approximately 44 male and female infants/neonates patients (<5 kg) are planned to be recruited in the study. There will be two sequential and age-descending cohorts of approximately 22 patients each (see [Figure 1-1](#)), all <5 kg: Cohort 1 of infants >28 days of age, and Cohort 2 of neonates ≤ 28 days of age. Cohort 2 will include 3 age subgroups (15-28, 8-14 and 1-7 days), starting with the highest age subgroup in Cohort 2.1. The two lower age subgroups (i.e., 8-14 and 1-7 days) will be recruited in parallel. These two subgroups will be optional, depending on recruitment feasibility.

In the event of inadequate exposure (study protocol section 4.2), determined at predefined PK checkpoints (i.e., after the first 9 patients in Cohort 1, and after the first 3 patients and then the first 9 patients of Cohort 2 (1-28 days of age)), additional patients may be recruited up to a total of 98 patients across the 2 cohorts ([Figure 1-2](#)). An additional PK check may be performed after the first 9 patients of the 15-28 days age group in Cohort 2 have been recruited. For Cohort 2, if an adequate dose cannot be determined at all or if recruitment is not feasible in any of the 3 age subgroups, the cohort may be closed and 22 additional patients may be recruited in Cohort 1 up to a total of approximately 44 patients treated with the same dose (instead of the planned 22 patients). Cohort 2.3 will start recruitment after the dose used in Cohort 2.2 has been assessed to be appropriate.

[figure not shown]
Patients will be admitted to the hospital on or before Day 1 (see [Figure 1-1](#)). After meeting all the inclusion and exclusion criteria in the study, they will receive study drug. The starting dose regimen in Cohort 1 will be two dispersible tablets twice daily for three consecutive days. The dose must be preceded and/or followed as much as possible by food/drinks rich in fat, e.g. breast milk, or formula milk.

Patients will remain in the hospital under close supervision until they are discharged by the investigator or designee on Day 4. At the discretion of the investigator, patients may stay for a few additional days if needed. The patients will be then followed up at regular intervals until Day 43 (core follow-up), in order to assess study drug exposure, safety, tolerability and efficacy. If symptoms re-emerge outside the scheduled study visits, parents/legal guardians of the

[figure not shown]
patients will be instructed to contact the investigator. In case of treatment failure (as per WHO definition), rescue treatment according to local clinical practice will be provided.

Patients will then attend a long term safety follow-up visit [REDACTED]

Figure 1-1 Patient participation overview

In this study, a stepwise and sequential approach will be adopted in order to minimize the risk for patients ([Figure 1-2](#)).

Figure 1-2 Study flow chart

PK exposure checks (together with safety and efficacy data review as available) will be performed on a periodic basis to assess the dose included at the following timepoints:

- 1) once the first 9 patients in Cohort 1 have been dosed and followed up to Day 15,
- 2) once the first 3 patients in Cohort 2 (15-28 days age subgroup) have been dosed and followed up to Day 15,
- 3) once the first 9 patients in Cohort 2 (15-28 days age subgroup) have been dosed and followed up to Day 15. In case exposure data in the 9 patients from the 1-28 day subgroup are not sufficient to make a decision on dose selection (e.g., due to a significantly different exposure across age subgroups), as many additional patients as needed to reach a total of 9 (across Cohort 2.1 and 2.2) in the 15-28 day subgroup specifically will be recruited in Cohort 2.2 and treated with the same dose. An additional PK check will then be performed after these additional patients will have been followed up to Day 15.

A total of 9 patients in a defined age group should allow to confirm with reasonable confidence if ART C_{max} is within approximately 2-fold (safety interval) of the C_{max} which has been found to be safe and efficacious in previous studies; a total of 3 patients will however allow to check at an early stage if the ART C_{max} range is within the expected safety interval (Cohort 2 only).

An Independent Data Monitoring Committee (DMC) will review the PK, efficacy and safety data at these checks, and also at two planned interim data assessments, one between the two cohorts, and another one after all patients in Cohort 2 have completed Day 43 ([Figure 1-2](#)).

The interim data assessment based on Cohort 1 data will serve to determine the starting dose level for Cohort 2 (for further details see study protocol section 10.2.1).

Based on these checks, the dose being considered will be assessed as suitable or not for the subgroup of patients treated.

In Cohort 1:

- if the dose is deemed adequate in the first 9 patients (based on PK, safety and efficacy data review as available), additional patients will be recruited up to approximately 22 treated with the same dose level (expansion phase).
- if the dose is not adequate, the first set of 9 patients will be repeated, up to twice, using a different dose level, until a dose level is determined as suitable.

In Cohort 2:

- if the dose is deemed adequate in the 3 patients from the highest age subgroup (15-28 days), recruitment of 6 additional patients in the 1-28 day subgroup will be attempted.
- if the dose is not adequate, the first set of 3 patients from the highest age subgroup (15-28 days) will be repeated, up to twice, using a different dose level, until a dose level is determined as suitable. Then, recruitment of 6 additional patients in the 1-28 day subgroup will be attempted.
- Another PK check (together with safety and efficacy data as available) will then be performed when a total of 9 patients have been treated with the same suitable dose in the 1-28 day subgroup. In case exposure data from these 9 patients (1-28 day subgroup) is not sufficient to make a decision on dose selection, as many additional patients as needed to reach a total of 9 (across Cohort 2.1 and 2.2) in the 15-28 day subgroup specifically will be recruited in Cohort 2.2 and treated with the same dose. An additional PK check will then be performed after these additional patients will have been followed up to Day 15. If the former PK check shows that the dose is suitable for all subgroups, expansion of Cohort 2 will include all age subgroups. If it is unsuitable for any of the two lower age subgroups, no further patients will be recruited in this/these lower age subgroup(s), and further expansion of Cohort 2 will only include patients from the 15-28 day subgroup. In the case the dose is not confirmed as suitable for the highest age subgroup, a repeat run with 9 patients (3+6 patients) will be performed using a different dose.

In Cohort 2, if through the steps above, no suitable dose has been determined in the higher age subgroup (15-28 days), recruitment will be stopped in that cohort and an additional 22 patients will instead be recruited in Cohort 1 and treated with the dose that was deemed adequate in that cohort.

Once either cohort's expansion has been completed with approximately 22 patients treated with the same, suitable dose, or any of the alternative scenarios described above, patients will be followed up to Day 43, when the complete set of key efficacy and safety parameters and PK exposures will be assessed.

Note: Patients treated with dose levels deemed not suitable will also be closely followed up to Day 43 and at one year of age.

In the unlikely case when all the iterations described above would have to be implemented, a maximum of 98 patients would be recruited.

Randomization

Due to single arm, treatment randomization will not be performed in this study. But patient will be randomly allocated to PK scheme 1 or 2.

Interim analyses

There will be two planned interim assessments performed at :

1. after all patients in Cohort 1 have completed Day 43 (core study period), when key efficacy and safety parameters and PK exposure data will be assessed in order to determine whether to proceed to Cohort 2 and if so, to select the starting dose for that Cohort.
2. after all patients in Cohort 2 have completed Day 43 (core study period). Efficacy and safety parameters and PK exposure data from both cohorts will be assessed.

Optional interim assessment

Additional interim assessments along with DMC reviews may be conducted to support decision making for dose recommendations.

1.2 Study objectives and endpoints

Table 1-1 Objectives and related endpoints

Objective(s)	Endpoint(s)
Primary objective(s)	Endpoint(s) for primary objective(s)

To assess the key PK parameter of artemether in infants and neonates < 5 kg body weight dosed with the new formulation of artemether-lumefantrine dispersible tablet	
Artemether C_{max} (represents the higher concentration between the concentrations at 1 hour and 2 hours after first dose)
Secondary objective(s)	Endpoint(s) for secondary objective(s)

To assess other key PK parameters of artemether, DHA and lumefantrine in infants and neonates <5 kg body weight dosed with the new formulation of artemether-lumefantrine dispersible tabletTo evaluate the safety and tolerability of the new formulation of artemether-lumefantrine dispersible tablet in infants and neonates <5 kg body weight with acute uncomplicated P. falciparum malariaTo determine the efficacy of the new formulation of artemether-lumefantrine dispersible tablet for treatment of acute uncomplicated P. falciparum malaria in infants and neonates <5 kg body weight	
Lumefantrine Day 8 concentration (C_{168h}) Artemether AUC, DHA and Lumefantrine C_{max} and AUC as appropriateSerious adverse events (SAEs), adverse events (AEs), and routine safety laboratory assessmentsPCR-corrected Adequate Clinical and Parasitological Response (ACPR) at Days 15, 29, and 43 Uncorrected ACPR at Days 8, 15, 29, and 43

Objective(s)	Endpoint(s)
	Incidence rate of recrudescence and new infections at Days 15, 29 and 43 Parasite and Fever clearance Times (PCT and FCT)

2 Statistical methods

2.1 Data analysis general information

Data will be analyzed by [REDACTED] on behalf of Novartis after the final DBL using SAS version 9.4 according to the data analysis presented in Section 12 of the study protocol which will also be available in [Appendix 16.1.1 of the CSR](#). Important information is given in the following sections and details will be provided, as applicable, in [Appendix 16.1.9 of the CSR](#).

There will be two planned interim assessments, one after Cohort 1, the second one after Cohort 2. More details can be found in [Section 2.12](#).

Data analyses required for the interim assessments will also be analyzed by [REDACTED] and corresponding outputs will be provided to the DMC. Outputs for the DMC will be part of the CSR shell document. No separate SAP or TFL shell document will be prepared.

After the first 9 patients in Cohort 1 and the first 3 and 9 patients in the higher age subgroup of Cohort 2 (1-28 days) and after the first 3 patients in the 2 younger subgroups of Cohort 2 (if they are recruited) have been treated with the same dose and followed up for at least 2 weeks (and optionally once 9 patients from the age group 15-28 days have completed Day 15), the database will be cleaned reasonably, data management reports using the raw data will be used for the regular review meetings and PK summaries will be generated by Novartis PK scientist.

Statistical analyses will be performed by cohort and treatment group. If there are treatment groups that are used for multiple cohorts, descriptive statistics will be calculated for these treatment groups by pooling data from all cohorts for the primary and key secondary endpoints.

Unless otherwise stated, summary tables/figures/listings will be on all patients included in the population under consideration.

Categorical data will be summarized as frequencies and percentages. For continuous data mean, standard deviation, median, minimum, and maximum will be presented. For selected parameters, the 25th and 75th percentile will also be presented.

There is no stratification done in this study.

2.1.1 General definitions

Study treatment: COA566 (artemether: lumefantrine 2.5 mg:30 mg dispersible tablet) is the investigation treatment. As this is a single-arm study there is no control treatment. COA566 is referred to as study treatment in the document.

Treatment group: Treatment group in this study means study drug dose level. Note that although there is only one study treatment, there are 4 possible dose levels (1 to 4 tablets per dose). The treatment group label will always include the study drug level even if there is only one study drug dose level in the whole study. In case that the dose level that passed the exposure check for the first 3 patients in the highest age subgroup in Cohort 2 is not appropriate for either or both the lower age subgroup(s) after the exposure check in 3 patients, the recruitment in these subgroup(s) will be stopped, they will be separated out from Cohort 2 and analyzed separately as needed.

Date of first administration of study treatment: The date of first intake of study treatment within the study.

Date of last administration of study treatment: The date of last intake of study treatment within the study.

Baseline: The last available measurement prior to first administration of study treatment.

Study day: The day of first administration of study treatment is defined as Day 1 (opposed to WHO terminology where this would be Day 0). Day -1 will be the day before Day 1. Day 0 does not exist.

Core period: Core period of the study starting with (and including) Day 1 until (and including) Day 43.

Parasitaemia: *P. falciparum* asexual parasite count greater than zero.

2.1.1.1 Clearance and treatment failure definitions

Fever Clearance time (FCT), defined as time from the first dose until the first time the axillary body temperature decreased below and remained below 37.5°C axillary or 38.0°C oral/tympanic/rectal for at least a further 24 hours. Note: 38.0°C is the temperature threshold for fever using oral/tympanic/rectal, which will be also used in the treatment failure definition.

Parasite clearance time (PCT), defined as time from the first dose until the first total and continued disappearance of asexual parasite forms which remained at least a further 48 hours.

Early Treatment Failure (ETF)

- Development of danger signs or severe malaria on Day 2, Day 3, Day 4 in the presence of parasitaemia.

- Parasitaemia on Day 3 higher than Day 1 count irrespective of axillary temperature.
- Parasitaemia on Day 4 with axillary temperature $\geq 37.5^\circ$.
- Parasitaemia on Day 4 equals to or more than 25% of count on Day 1.

Late Clinical Failure (LCF)

- Development of danger signs or severe malaria on any day from Day 5 to Day 43 in the presence of parasitaemia without previously meeting any of the criteria of Early Treatment Failure.
- Presence of parasitaemia and axillary temperature $\geq 37.5^\circ$ on any day from Day 5 to Day 43 without previously meeting any of the criteria of Early Treatment Failure.

Late Parasitological Failure (LPF)

- Presence of parasitaemia on any day from Day 8 to Day 43 and axillary temperature $<37.5^\circ$ without previously meeting any of the criteria of Early Treatment Failure or Late Clinical Failure.

2.2 Analysis sets

The Full Analysis Set (FAS) comprises all subjects that received any study drug and had *Plasmodium falciparum* present at Screening visit. Subjects will be analyzed according to the treatment(s) received as per protocol.

The Safety Set includes all subjects who received at least one dose of study treatment. Subjects will be analyzed according to the study treatment received as per protocol. The Safety Set will be used for safety analyses while FAS will be used for other analyses.

The Per-Protocol Set (PPS) is a subset of subjects of the Full Analysis Set and is characterized by the following criteria:

- did not have important protocol deviations affecting efficacy
- took at least 80% of study medication
- PCR corrected cure status at Day 29 can be defined.

Important protocol deviations for exclusion from the PPS will be identified by the clinical team before database lock.

The PK set is a subset of the Full Analysis Set who had evaluable PK parameter data.

2.2.1 Subgroup of interest

Not applicable.

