|-------|-------------------|---------------|----|---|-----------------------------|--------------------------|
| B2306 | <5kg >28days | 20 | 18 | 509 ± 309 | 6.38 | 815 |
| B2303 | ≥5 - <15 | 20 | 55 | 196 ± 204 | 5.16 | 386 |
| B2303 | ≥15 - <25 | 40 | 29 | 150± 106 | 8.03 | |
| B2303 | ≥25 - <35 | 60 | 8 | 134 ± 56.7 | 12.3 | |

ART: artemether; LUM: lumefantrine

Based on the above data and on ontogeny data (course of development of the human organism), a full PBPK model was developed and validated. This model was used to simulate exposures to artemether and lumefantrine corresponding to different doses and at different neonate and infant ages (Report DMPK R1809279) (See [Table 4-2](#) below).

While selecting the doses for the present study, the following considerations were taken into account:

- due to artemether's potential neurotoxicity (based on animal data), it is hypothesized that its exposure should be contained within the range that has been found to be well tolerated and efficacious in children ≥ 5 kg.
- Exposure to lumefantrine should also be adequate, especially the Day 8 plasma concentration (which is a surrogate efficacy marker), i.e., it should be ≥ 200 ng/mL on

Day 8 based on an extensive meta-analysis, ([WWARN 2015](#)) to achieve long-term parasite clearance.

- within the exposures which were found to be well tolerated in children ≥ 5 kg BW, while kept on the higher side, due to lower immunity and potential lower exposure in pediatric patients ([Kloprogge et al 2018, WWARN 2015](#)).

Table 4-2 PBPK modeled exposures based on a 5:60 mg (A:L) dose regimen

| | Neonates (≤ 28 days, <5 kg) | Infants (>28 days (1-7 months), <5 kg) |
|--------------------------------------|-------------------------------------|---|
| Artemether (5 mg) | | |
| First dose C_{max} (ng/mL) | 234 | 78.5 |
| Lumefantrine (60 mg) | | |
| Full regimen C_{max} (μ g/mL) | 5.1 | 5.4 |
| C_{168h} (ng/mL)* | 530 | 270 |

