5.1 Inclusion criteria

Subjects eligible for inclusion in this study must meet **all** of the following criteria:

1. Male or female neonates / infants
2. Body weight <5 kg but ≥ 2 kg
3. In Cohort 1, infants aged >28 days; in Cohort 2, neonates aged 1 to ≤ 28 days (3 subgroups: 15-28 days; 8-14 days; 1-7 days)
4. Microscopically confirmed diagnosis of *P. falciparum* malaria (or mixed infections)
 - in Cohort 1: of ≥ 500 and $<100,000$ parasites/ μ L asexual *P. falciparum* parasitemia
 - in Cohort 2: of ≥ 100 and $<100,000$ parasites/ μ L asexual *P. falciparum* parasitemia
 - either congenital or neonatal
 - either symptomatic or asymptomatic
5. Parental/legal guardian informed consent obtained and signed prior to any study related procedure. If the parent/legal guardian is unable to read or write, then a witnessed consent according to local ethical standards is permitted (formally documented and witnessed, via an independent trusted witness)
6. The parent/legal guardian is able to understand and comply with protocol requirements, instructions and protocol-stated restrictions for their child and is likely to complete the study as planned

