2.5.2 Statistical hypothesis, model, and method of analysis

Ninety percent (90%) 2-sided confidence intervals for ART C_{max} for the geometric mean will be presented by cohort and treatment group. Calculation will be based on the log normal distribution. The study objective will be considered to be met if 90% CIs for ART C_{max} contain the desired values based on historical data especially those from children $\geq 5-15$ kg BW in Study B2303. The desired values are displayed in the Appendix in Table 5-7.

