3.1.1 Primary endpoint(s)

Artemether C_{max} (represents the higher concentration between the concentrations at 1 hour and 2 hours) after the first dose is the primary endpoint. The distribution of C_{max} is best described by log normal distribution. The half width of the 2-sided 90% confidence interval for log C_{max} is the target for sample size calculation. The relevant historical data for sample size calculation are the standard deviations of log C_{max} , which are usually invariant to the dosage (See [Table 3-1](#)).

Table 3-1 Standard deviation for log C_{max} in Coartem studies A2102 and B2306

Study and formulation of artemether-lumefantrine	Artemether C_{max}	Day 8 Lumefantrine concentration
A2102* (healthy volunteers) 80:480 mg tablet	0.58	-
A2102 (healthy volunteers) 4 tablets of 20:120 mg	0.52	-
B2306 (infants >28 days of age) 20:120 mg dispersible tablet	0.65	0.654

*Study CCOA566A2102; **Study CCOA566B2306

The table shows that the standard deviation for log C_{max} was about 12% to 25% higher for infants in Study B2306 than for healthy volunteers in Study A2102. The patient population in the current study (B2307) is similar to the patient population in Study B2306.

For log C_{max} , a standard deviation of 0.65 from Study B2306 will therefore be used. Based on the standard deviation of 0.65 in log scale, a sample size of 16 evaluable patients will provide 80% probability that the observed half width of 2-sided 90% CI for log C_{max} is ≤ 0.337 or 1.4 times (covering the targeted C_{max}) in terms of ratio (nQuery Advisor 8). This sample size is applied to each cohort.

PK sampling will be designed in order to get all patients evaluable for artemether C_{max} analysis. Taking into account about 10% of patients not evaluable for this PK analysis, about 18 patients should be enrolled in each cohort.

For each cohort the sample size will be increased slightly to allow for higher dropouts for the secondary endpoint, Day 8 (168 h) lumefantrine concentration (see [Section 3.1.2](#)).

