5.7 Statistical models

5.7.1 Primary analysis

The primary analysis is detailed in [Section 2.5](#).

The primary endpoint ART C_{max} will be displayed by cohort and treatment group using the geometric mean. The geometric mean will be calculated by deriving the mean of the log-transformed values followed by an exponential transformation, i.e. *Geometric Mean (GM) = e^{mean(log(x))}* with x = ART C_{max} of a participant.

Corresponding 2-sided 90% confidence intervals for the GM will be calculated assuming a log normal distribution of the primary endpoint. The lower and upper limits will be calculated as follows:

$$\exp(\bar{x} \pm t_{(1-\frac{\alpha}{2};n-1)} \times \frac{s}{\sqrt{n}})$$

with \bar{x} = the arithmetic mean of the log-transformed endpoint, $t_{(1-\frac{\alpha}{2};n-1)}$ = the $(1 - \frac{\alpha}{2})$ critical value of the Student's t statistic with $n - 1$ degrees of freedom, s = the standard deviation of the log-transformed endpoint, and n = the number of patients with available endpoint in the corresponding cohort and treatment group.

The logarithm to the natural base is used.

The calculation will be implemented in SAS using PROC MEANS on log data followed by an exponential transformation.

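### No PK summary by neonatal age subgroup or mg/kg is planned, although dose suitability is decided by age subgroup, so an excess in a few of the youngest can stay hidden in the Cohort 2 interval

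*SAP*

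**What the plan says.** **Level of analysis.** SAP 2.2.1 ("Subgroup of interest") declares none. For the primary endpoint, SAP 2.5.2 states that "confidence intervals for ART C_{max} for the geometric mean will be presented by cohort and treatment group", where treatment group means dose level (SAP 2.1.1). SAP 2.6.2 (Day 8 lumefantrine) and 2.9 (other PK) use the same level. The success rule is "The study objective will be considered to be met if 90% CIs for ART C_{max} contain the desired values based on historical data". The reference geometric mean for children of 5 to <15 kg in B2303 is 101 ng/mL; it stands in SAP Table 5-6, although 2.5.2 points to Table 5-7.

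**Level of decision.** Protocol section 3 and SAP 1.1 split Cohort 2 into 15-28, 8-14 and 1-7 days and decide suitability by subgroup: "If it is unsuitable for any of the two lower age subgroups, no further patients will be recruited in this/these lower age subgroup(s". The two younger subgroups are optional.

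**Dose and size.** Eligibility is "Body weight <5 kg but ≥ 2 kg" (Protocol 5.1), and the dose is a fixed number of tablets (Protocol 6.1.3, Table 6-3).

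**Separation of a subgroup.** The opening text of Protocol section 12 and SAP 2.1.1 say that a lower-age subgroup found inappropriate after an exposure check in 3 patients is stopped, taken out of Cohort 2 and analysed separately where needed. Protocol 12.5.3 and SAP 2.1 also mention a check of the first 3 patients in each younger subgroup. The list of checks in Protocol section 3 and the text of 12.7 have no such check. Their 3-patient check is for 15-28 days only, and the 9-patient check pools 1-28 days.

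**The concern.** The trial exists because artemether exposure was too high in a small, young population. Protocol 4.2 links that to immature metabolic enzymes and calls confidence in the predictions moderate, least so in the youngest. Protocol section 3 itself allows for materially different exposure across the neonatal subgroups. The plan nevertheless has no routine display of either main PK endpoint at the level where it expects differences and takes decisions.

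Whether a subgroup is ever reported on its own depends on a check with no stated numerical trigger, and the documents disagree on whether that check is run. If it is not run, or is passed by chance, the subgroup's values enter the Cohort 2 geometric mean. A criterion that asks only whether the interval contains the reference is then weak protection: differences between subgroups widen the interval and make containment easier.

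**Working it through.** **1. The plan's own figure.** "a standard deviation of 0.65 from Study B2306 will therefore be used" (SAP 3.1.1), with 16 evaluable patients, a target half-width of 0.337 (exp 0.337 = 1.40) and 80% probability.

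P(half-width ≤ w) = P(χ² with n−1 df ≤ (n−1)·n·w² / (t²·s²)), where t is the 0.95 quantile on n−1 df.

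For n = 16, t = 1.753, s = 0.65: 15 × 16 × 0.337² / (1.753² × 0.65²) ≈ 21.0, giving 86%. Conditional on the interval covering the true mean, it is 85%. The smallest n reaching 80% is 15 unconditionally (80.2%) and 16 conditionally (n = 15 gives 78.7%). The planned 16 therefore reproduces as the smallest n under the conditional definition.

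**2. Dose per kg.** 5 mg / 2 kg = 2.5 mg/kg. Just under 5 kg the figure is just over 5/5 = 1.0 mg/kg. The span is up to 2.5-fold, and is the same for any fixed tablet count.

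**3. Illustration for Cohort 2.** Assume k of 16 evaluable neonates have a true geometric mean of 3 × 101 = 303 ng/mL, the others 101, with log SD 0.65 within each group. The interval is that of SAP 5.7.1: "Corresponding 2-sided 90% confidence intervals for the GM will be calculated assuming a log normal distribution of the primary endpoint".

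For k = 4:
- Geometric mean = 101 × 3^(4/16) = 133.
- Pooled log SD = √(0.65² + (16/15) × 0.25 × 0.75 × (ln 3)²) = 0.815.
- Half-width = 1.753 × 0.815 / √16 = 0.357.
- 90% CI = 133 × exp(±0.357) = 93 to 190, which contains 101.

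The last column comes from 300,000 simulated trials per row.

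| k of 16 at 3× | Expected GM | 90% CI | Criterion met |
|---|---|---|---|
| 0 | 101 | – | 90% |
| 3 | 124 | 88-175 | 78% |
| 4 | 133 | 93-190 | 67% |
| 5 | 142 | 99-205 | 54% |
| 6 | 152 | 105-221 | 40% |

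**4. Sensitivity.** With 22 evaluable patients the criterion is met in 72% of trials for k = 4 and 49% for k = 6. With 16 patients and the others at 0.7 × reference, it is met in 98% for k = 4 and 91% for k = 6. With the whole cohort at 3×, it is met in under 0.01%.

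**5. If a 3-patient check is run.** The documents give no formula. Reading it as an observed geometric mean no more than 2-fold above reference, a true 3-fold subgroup passes with probability Φ((ln 2 − ln 3) / (0.65/√3)) = Φ(−1.08) = 14%. It passes both this check and the cohort criterion (k = 3 of 16) in 12% of trials.

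**6. What a separate summary would show.** At a true 303 ng/mL and log SD 0.65, n = 4 gives half-width 2.353 × 0.65 / 2 = 0.765, so the 90% CI is 141 to 651. For n = 3 it is 101 to 906, and such an interval still contains 101 in 40% of trials (18% at n = 4).

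**The case against.** Several stronger readings are tempting, and the documents do not support them.

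- *All neonates are always pooled.* A reader might infer this from SAP 2.2.1, but Protocol section 12 and SAP 2.1.1 take out a subgroup that fails its check, and results are split by dose level.
- *The youngest are predicted to be 3-fold over-exposed.* Table 4-2 gives 234 ng/mL for all neonates against 78.5 for older infants. The ratio 234/78.5 = 2.98 compares those two broad groups, and no value is given for any neonatal subgroup. Against the reference, 234/101 = 2.3. If all 16 neonates were at 234, the interval would be 234 × exp(±0.285) = 176 to 311, and the criterion would show the excess.
- *Subgroup suitability is read off the Cohort 2 mean.* It is not. It comes from PK checks reviewed by the DMC with safety and efficacy data. The interval rule decides only whether the study objective is met.
- *Age and weight can enter no PK analysis.* The physiological model, built to simulate exposure by age, is to be updated with trial data (Protocol 4.2, 4.4), and further modelling is allowed. SAP 2.9 lists Cmax by subject and reports the maximum and CV. Protocol 12.6 is redacted and the readable SAP has no section 2.11, so total absence cannot be asserted.

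These points remove any claim of a predicted harm or of a wrong decision rule. They do not supply the missing summary. Subject listings and an optional model update are not a pre-specified result by subgroup, and separation depends on a check with no stated trigger and inconsistent scheduling.

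**Conclusion.** The point holds as a gap in planned reporting. In the readable text neither artemether Cmax nor Day 8 lumefantrine has a routine summary by neonatal age subgroup, weight or mg/kg, although suitability is decided by age subgroup. A subgroup that passes its check, or never gets one, stays in the pooled Cohort 2 estimate.

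The size depends on assumptions the documents do not make: a 3-fold excess in a few neonates, the others at reference and log SD 0.65. On those terms the criterion is met in 78%, 67%, 54% and 40% of trials with 3, 4, 5 and 6 such infants out of 16, against 90% with no excess. These figures apply when no separate check intervenes; a check read as in step 5 of the working would cut the risk substantially. The younger subgroups are optional and may be very small. No calculation was made for lumefantrine. This is a cheap improvement, not a flaw that invalidates the primary analysis.

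**What to change.** In SAP 2.2.1, 2.5.4, 2.6 and 2.9, pre-specify for each dose level:

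- n, geometric mean, 90% CI and individual values of artemether Cmax and Day 8 lumefantrine for 1-7, 8-14, 15-28 and >28 days;
- plots of both endpoints against age in days and against mg/kg;
- as support only, an exploratory regression of each log endpoint on age and log weight, with predictions kept within the age-weight combinations observed.

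Report the cohort-level criterion together with these subgroup results. Separate reporting then no longer hangs on an undefined trigger.

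Reconcile Protocol section 3 and 12.7 with the opening of Protocol section 12, Protocol 12.5.3 and SAP 2.1 and 2.1.1 on whether the younger subgroups have their own PK check. In the same pass, reconcile SAP 1.1, which labels the 9-patient check 15-28 days, with the protocol's 1-28 days.

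Cost: one table, a few plots and one small model, from age and weight already recorded (Protocol 8.2). The drawback is imprecision: at three or four infants the intervals are wide and should be labelled descriptive. No dose or suitability rule is proposed here.
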